The subject will be asked to undergo an MRI through the study team at the Center for Translational Imaging at Northwestern University. Before the study participant completes the MRI, he or she must answer questions about their medical and surgical history on a MRI safety questionnaire to determine whether it will be safe for them to complete the MRI. If not, they will not be eligible to participate in this study. No contrast will be administered. The MRI images will be de-identified and electronically transmitted to a secure file transfer (SFT) system to the University of Florida for interpretation.

Before dosing occurs, a member of the study team (physical or occupational therapist) will complete the following functional assessments: Northstar Assessment for Dysferlinopathy (NSAD) –AMB, 10 meter timed run test and 6-minute walk test if the patient is ambulatory, performance of upper limb (PUL) evaluation, Brookes and Vignos scales. A member of the study team will also collect the strength assessment, MMT MRC.

Subjects will be asked to complete two questionnaires; ACTIVLM and a Quality of Life Questionnaire.

The subject will also complete a bone density (DEXA) scan at Northwestern Memorial Hospital.

Monthly Phone Calls

Between Day 0 and Month 6, a member of the study team will call the subjects on a monthly basis to determine their state of health and whether they are taking the medication correctly. State of health will be determined by assessed by asking if the subject has experienced any changes to their physical health (adverse events). He or she will also ask the subjects about how they are taking the medication and if you are doing so correctly. If the subjects are not, the study member will help the subjects by providing additional instructions on how to correctly take the study drug.

Month 6

After 6 months of treatment, subjects will return to the MDA Clinic at Northwestern Memorial Hospital. A member of the study team will collect vital signs, weight and height, medical history, concomitant medication information, and review adverse events. The subject will also provide a sample for safety laboratory analysis (Comprehensive chemistry panel, hemoglobin A1C, CK, and lipid panel). A blood and urine sample will be taken for exploratory biomarkers.

A member of the study team will also collect forced vital capacity in a sitting and supine position.

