A member of the study team (physical or occupational therapist) will complete the following functional assessments: Northstar Assessment for Dysferlinopathy (NSAD) –AMB, 10 meter timed run test and 6-minute walk test if the patient is ambulatory, performance of upper limb (PUL) evaluation, Brookes and Vignos scales. A member of the study team will also collect the strength assessment, MMT MRC.

Subjects will be asked to complete two questionnaires; ACTIVLM and a Quality of Life Questionnaire.

The subject will also complete a bone density (DEXA) scan at Northwestern Memorial Hospital.

An MRI will be conducted at the Center for Translational Imaging at Northwestern University within 2 weeks before or after the subject’s final visit. No contrast will be administered.

An overview of the study assessments may be found in Table 1.0 below:

| | Screening (D0-2M) | Day 0 | M6 +2 wks |
|--------------------------------------|-------------------|-------|-----------|
| Informed Consent | X | | |
| Demographics | X | | |
| Vital Signs | X | X | X |
| Weight and Height | X | X | X |
| Medical History | X | X | X |
| Concomitant Medications | X | X | X |
| Genetic mutation Confirmation | X | | |
| Review EKG* | X | | |
| Review Echo** | X | | |
| Safety Monitoring Labs*** | | X | X |
| Forced Vital Capacity (FVC) | | X | X |
| NSAD | | X | X |
| 6-min Walk Test / 10 m Run | | X | X |
| Performance of Upper Limb | | X | X |
| Brooke Scale | | X | X |
| Vignos Scale | | X | X |
| MMT MRC | | X | X |
| Grip Strength | | X | X |
| ACTIVLM | | X | X |
| Quality of Life Questionnaire (SF36) | | X | X |
| MRI/MRS | | X | X |
| DEXA Scan | | X | X |
| Study Drug Dispensation | | X | |
| Review of Adverse Events | | | X |

Table 1.0: Schedule of Assessments from Screening, Day 0, and Month 6

* EKG – Results within 2 months of study initiation accepted

**Echo – Results within 6 month of study initiation accepted

*** Comprehensive chemistry panel, hemoglobin A1C, CK, lipid panel

SHARING RESULTS WITH PARTICIPANTS

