Results of investigational diagnostic tests, and incidental findings, will be shared with the subjects through the MyChart patient portal. Once the laboratory samples are drawn and analyzed by the Northwestern Memorial Hospital Main Laboratory, the results will be posted to MyChart. If the results are abnormal and clinically significant, the Principal Investigator will notify the subject about further testing and treatment. Furthermore, the Principal Investigator will contact and inform the subject's primary care physician.

Results from questionnaires, functional assessments, blood / urine exploratory biomarkers, DEXA, and MRI imaging will not be shared with the patient.

STUDY TIMELINES

The study team will screen and enroll subjects for a period no longer than 1 year from IRB approval.

Screening will occur at one clinic visit that will last no more than 2 hours. If subjects have not had a MRI within the previous 6 months, they will return for a MRI (1 hour). Similarly, if subjects have not had a DEXA scan within the previous 6 months, they will return for a DEXA scan (1 hour).

Enrolled subjects will participate in the study for 6 months from their first dosing (Day 0). Subjects will schedule their MRI and DEXA scan on the final day of the study. If subjects are unable to complete a MRI or DEXA on that day, they will return to complete the required procedure within the next 2 weeks.

The investigators estimate the study's primary analyses will be completed by December 2019.

INCLUSION AND EXCLUSION CRITERIA

Inclusion criteria (Collected at screening):

1. Patients with Becker muscular dystrophy or LGMD2A (CAPN3), LGMD 2B (DYSF), LGMD 2C (SGCG), LGMD2E (SGCB), LGMD2F (SGCD), LGMD 2I (FKRP), LGMD (ANO5). Genetic mutation or muscle biopsy staining required to confirm genetic subtype
2. Ages 18-65 years
3. EKG without evidence of prior infarct or atrial fibrillation done within 2 months of study initiation.
4. Echocardiogram with LVEF >25% done within 6 months of study initiation.
5. Stable medications (same medication and dose) for the previous 3 months
6. Stable pulmonary status for the previous 6 months (No change in FVC by more than 20% in the past 6-months)

Exclusion criteria (Collected at screening):

1. Diabetes
2. BMI>35 kg/m²
3. Cardiac transplantation
4. Myocardia Infarct in the past 2-years from screening
5. Any history of tuberculosis
6. Untreated or uncontrolled (medication and/or dose change in previous month from screening) hypertension

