Some people cannot have an MRI because they have certain types of metal in their body. For instance, if you have a heart pacemaker, artificial heart valves, metal implants such as metal ear implants, bullet pieces, chemotherapy or insulin pumps or any other metal such as metal clips or rings, you cannot have an MRI. During this test, subjects will lie in a small closed area inside a large magnetic tube. Some people are scared or anxious in small places (claustrophobic). The MRI scanner makes loud banging noises while taking a measurement, so either ear plugs or specially designed headphones will be used to reduce the noise.

Risks from DEXA bone scans

Procedures such as CT scans, X-rays and/or radioactive drugs will be used during this research study to see how subjects are doing. The cumulative radiation exposure from these tests is considered small and is not likely to adversely affect subjects or their disease. However, the effects of radiation add up over a lifetime. It is possible that having several of these tests may add to subjects' risk of injury or disease. When deciding to enter this study, subjects will think about their past and future contact with radiation. Examples of contact with radiation include x-rays taken for any reason or radiation therapy for cancer treatment.

Background radiation is present on Earth (soil, air, water, food) and also includes cosmic radiation. Exposure to radiation from natural sources is a feature of everyday life. Your

participation in this study will involve additional exposure to radiation. The radiation dose received for one DEXA scan is approximately equal to 4.5 days of background radiation.

The effective dose for one DEXA scan (lumbar spine and total hip) is 4 mrem. The total effective dose of all research related radiation procedures is 8 mrem.

POTENTIAL BENEFITS TO PARTICIPANTS

There may be benefit from participating in this research. Potential benefit may include increased strength and muscle mass.

DATA MANAGEMENT AND CONFIDENTIALITY

This is a pilot study to determine safety and tolerability of the intervention. All subjects will receive once weekly prednisone, and no placebo arm is planned for this study. Data will be compared between study entry and 6 months of once weekly steroids. The data from this study will be used to plan for a larger trial. In preclinical animal models, a 25% improvement in muscle strength and function was observed.

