During the trial, study team members with access to Northwestern Memorial Hospital's electronic medical records System, Epic, will have access to the subject's medical chart. The study team will print, redact, and store all study-specific test results in the subject binders. All medical records will be de-identified and labeled with the subject identification number. The tests obtained from Epic include: genetic test results, medical history, concomitant medications, safety laboratory results, EKG results, Echo results, DEXA results, and MRI results. The remaining tests will be performed during the study visit and documented on case report forms (source documentation) located in the subject binders.

MRI images that are collected as part of this research study will be obtained at the Center for Translational Imaging and Northwestern University. The study team will obtain a de-identified copy of the MRI images for all study participants that contains the participant's study number. A member of the study team will transmit the images to the University of Florida through a secure file transfer (SFT) system. Copies of the images will also be secured by the study team in the subject binders.

The Principal Investigator and study team will have access to the data and be responsible for data transmission and storage.

The study binders will be secured in [name] and, upon completion of the trial, O'Hare Storage Facility. Study data will be stored for a period no longer than 5 years. After this period, unless otherwise notified by the study team, all study records will be shredded or disposed through HIPAA-compliant document bins.

PROVISIONS TO PROTECT THE PRIVACY INTERESTS OF PARTICIPANTS

The Principal Investigator and study team will make every effort to ensure that the subjects' privacy is protected. As mentioned above, subjects will only share personal information with the Principal Investigator and members of the study team. The study team will be permitted to access sources of information about the participant through the consent. During the consent process, and throughout the study, subjects will be given the opportunity to ask questions about the study and voice their concerns. Contact information will be provided to the subjects in the consent.

COMPENSATION FOR RESEARCH-RELATED INJURY

Subjects will not be compensated for research-related injury.

ECONOMIC BURDEN TO PARTICIPANTS

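### STUDY TIMELINES implies that a subject with an MRI or DEXA in the previous 6 months can skip the baseline scan, while the Day 0 procedures and Table 1.0 set both scans for every subject

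*Protocol*

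**What the plan says.** STUDY TIMELINES, in its paragraph on screening, makes the return visit for each scan conditional. For MRI: "If subjects have not had a MRI within the previous 6 months, they will return for a MRI (1 hour"). For DEXA: "if subjects have not had a DEXA scan within the previous 6 months, they will return for a DEXA scan (1 hour").

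Other parts of the protocol carry no such condition:

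- PROCEDURES INVOLVED, Day 0, on MRI: "The subject will be asked to undergo an MRI through the study team at the Center for Translational Imaging at Northwestern University". On DEXA: "The subject will also complete a bone density (DEXA) scan at Northwestern Memorial Hospital".
- Table 1.0 marks MRI/MRS and DEXA at Day 0 and at Month 6, and neither at screening. Its footnotes accept earlier results for two tests only: EKG ("Results within 2 months of study initiation accepted") and echocardiogram ("Results within 6 month of study initiation accepted").
- The design summary under BACKGROUND places an MRI/MRS before the start of prednisone and another at 6 months.
- STUDY ENDPOINTS lists DEXA and the MRI/MRS comparison at screening and 6 months, and names muscle volume, T2 and fat fraction as the MRI/MRS measures.
- DATA MANAGEMENT AND CONFIDENTIALITY: "MRI images that are collected as part of this research study will be obtained at the Center for Translational Imaging and Northwestern University". On the analysis: "Data will be compared between study entry and 6 months of once weekly steroids". The same section says that no placebo arm is planned.

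**The concern.** A condition on who returns for a scan has effect only if some subjects do not return. Read plainly, STUDY TIMELINES waives the baseline scan for anyone scanned in the previous 6 months, and no other section allows this. It does not say which scan is then the baseline, whether the 6 months run back from screening or from Day 0, or whether the earlier scan must contain the measures listed in STUDY ENDPOINTS.

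Change in MRI muscle mass is a secondary outcome, judged within subjects in a single arm. A baseline made months before the first dose would add untreated disease course to the change score, by an amount that differs between subjects, and no control group could remove it. An earlier scan might also lack volume, T2, fat fraction or MRS, and the subject would then have no usable change. DEXA has the same timing problem. It is not in the list of outcome measures, but it is collected at both times, and RISKS TO PARTICIPANTS names loss of bone density as a steroid risk.

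**Working it through.** **1. The stated radiation dose.** RISKS TO PARTICIPANTS gives 4 mrem per DEXA and 8 mrem for all research radiation.

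- DEXA at Day 0 and Month 6: 2 × 4 = 8 mrem, the stated total.
- Baseline DEXA waived: 1 × 4 = 4 mrem, which fits only if 8 is a ceiling.
- An extra screening DEXA on top of the Day 0 scan: 3 × 4 = 12 mrem, above the stated total.

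The figure agrees with two research DEXA scans per subject. It does not exclude a waiver, but it does count against a third scan.

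**2. Interval between scans.** Let a be the age of the baseline scan at Day 0 in months, and w the offset of the final scan from Month 6. STUDY TIMELINES puts the final scan on the last study day or within the next 2 weeks, so w = 0 to 0.5 (2 weeks taken as 0.5 month). The Month 6 text also allows the MRI up to 2 weeks before the final visit, w = −0.5.

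Interval = a + 6 + w. Share before treatment = a / (a + 6 + w).

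| a | w = 0 | w = 0.5 | w = −0.5 (MRI only) |
|---|---|---|---|
| 0 | 6 months, 0% | 6.5 months, 0% | 5.5 months, 0% |
| 3 | 9 months, 3/9 = 33% | 9.5 months, 3/9.5 = 32% | 8.5 months, 3/8.5 = 35% |
| 6 | 12 months, 6/12 = 50% | 12.5 months, 6/12.5 = 48% | 11.5 months, 6/11.5 = 52% |
| 8 | 14 months, 8/14 = 57% | 14.5 months, 8/14.5 = 55% | 13.5 months, 8/13.5 = 59% |

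The row a = 0 is the Day 0 schedule. The row a = 3 is only an illustration. The row a = 6 counts the look-back from Day 0. The row a = 8 counts it from a screening visit 2 months before Day 0, reading the Table 1.0 heading 'D0-2M' as a 2-month screening window (an assumption).

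On that same reading, the words 'at screening' in STUDY ENDPOINTS could by themselves allow 2 untreated months: 2/8 = 25%.

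**3. Effect on the mean change.** The protocol gives no rate of progression. Assume a constant untreated change of r per month, and let k of the 30 subjects have a baseline scan 6 months old at Day 0. Each such subject's change gains 6r, as much as the untreated change over the whole 6-month treatment period. The mean shifts by (k/30) × 6r = 0.2k × r:

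- k = 0: no shift
- k = 5: 1r
- k = 15: 3r

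For scans 8 months old the shift is (k/30) × 8r, which is 4r at k = 15. Both k and r are assumptions.

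**The case against.** The strongest reply is that STUDY TIMELINES describes visits and burden and nowhere calls an earlier scan the baseline. The Day 0 text, Table 1.0 and the design summary all have the MRI made in the study before dosing, so staff who follow the schedule would scan everyone. This stands as a limit on the consequence: reuse is inferred, and it may never happen. It does not remove the conflict, because staff who follow STUDY TIMELINES would do otherwise.

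A second reply is that the look-back might serve eligibility, since ability to complete MRI and osteoporosis risk are both judged at screening. The protocol does not support this. Table 1.0 has no scan at screening, and for DEXA an added screening scan would bring the dose to 12 mrem against the stated 8.

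Some of the supporting text is weaker than it looks. Study entry is not defined. An earlier MRI could have been made at the same imaging centre. DATA MANAGEMENT AND CONFIDENTIALITY also lists MRI and DEXA among the results taken from the medical record, which could point either way. It is also fair that a contradiction can be resolved in either direction: the protocol could instead state when an earlier scan is acceptable. That would settle the text but leave the untreated interval in the change score. Finally, this is a pilot and the outcome is secondary, which limits the weight of the point.

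**Conclusion.** The concern holds. The conditional sentences in STUDY TIMELINES cannot be reconciled with the Day 0 procedures and Table 1.0, and the contradiction should be fixed.

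The certainty attaches to the conflict in the text. The bias is conditional on an earlier scan being used as baseline. In that case, for a scan 6 months old at Day 0, about half of the interval measured is untreated; if the look-back runs from screening, the share is somewhat more than half. The shift in the mean cannot be given a value, because neither the progression rate nor the number of such subjects is in the protocol. It is nil if no one is affected. The primary safety measures, laboratory tests and FVC, are not involved. An analysis plan could not repair the problem afterwards, because a Day 0 scan that was not made cannot be recovered.

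**What to change.** - Delete the two conditional sentences on MRI and DEXA in STUDY TIMELINES.
- State there that every subject has the baseline MRI/MRS and DEXA under the study procedures at Day 0, before the first dose, in line with PROCEDURES INVOLVED and Table 1.0.
- In STUDY ENDPOINTS, change the baseline time point for the MRI/MRS comparison and the DEXA from screening to Day 0.
- If an earlier scan has already served as baseline for anyone, report the MRI and DEXA changes with and without those subjects.

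The cost is a short amendment and one 1-hour visit for each scan that would otherwise have been reused. Table 1.0 already schedules those scans. A baseline DEXA adds 4 mrem, within the stated total of 8 mrem.

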We propose to carry out an open label safety and efficacy trial of oral weekly GC steroids in patients with BMD and LGMD subtypes. Subjects will be recruited based on age, molecular diagnosis of BMD and LGMD subtypes, and willingness to participate. Both ambulatory and nonambulatory subjects will be included. Subjects will be excluded if they have diabetes mellitus, full time ventilator use, or severely compromised cardiac function, including symptoms referable to heart failure. Subjects must provide consent.

Subjects will be asked to take weekly GC oral prednisone dosed based on weight (1mg/kg for patients who weigh less than or equal to 70 kg and 0.75 mg/kg for patients who weigh more than 70 kg). Subjects will also be instructed to take their weekly prednisone on Mondays after their last meal between 7 and 9 PM. Prior to initiation, subjects will provide a blood sample for baseline screening including serum chemistries, HgbA1-C, creatine kinase, and lipid panel (HDL, LDL, triglycerides, and total cholesterol) and for exploratory biomarkers. Subjects will also provide a urine sample to analyze changes in metabolic biomarkers that are excreted. Subjects will have a physical exam and medical record review. Subjects will have strength testing and complete 10 meter timed run test in addition to a 6 min walk test (if ambulatory). Subjects will be asked to complete quality of life questionnaire. At 6 months, subjects will be evaluated with physical exam, strength testing, spirometry, 10 meter timed run test and 6 min

walk test (if ambulatory), blood draw for serum chemistry, HgbA1-C, creatine kinase, lipid panel and for exploratory biomarkers. Subjects will also provide a urine specimen to be analyzed for any changes in excretion of metabolic markers as an exploratory endpoint. Subjects will be asked to complete a quality of life questionnaire. An MRI/ MRS will be performed before starting GC oral prednisone and at 6 months.

STUDY ENDPOINTS:

Primary Outcome: Safety

Safety monitoring:

- Comprehensive chemistry panel, hemoglobin A1C, CK, lipid panel at screening and after 6 months of GC steroid dosing
- FVC (sitting, supine) at screening and at 6 months
- Phone calls to each patient each month to determine their state of health and study drug compliance.

Secondary Outcomes: Change in MRI muscle mass, improved muscle performance, improved quality of life, blood and urine metabolic biomarker changes.

Functional Assessments

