- NSAD (Northstar Assessment for Dysferlinopathy)—AMB
- 6 min walk test and 10 meter timed run test, if patient ambulatory
- PUL (Performance of Upper Limb)
- Brooke Scale
- Vignos Scale

Strength assessments

- MMT MRC

Patient Reported Outcome Measures

- PROM: ACTIVLM
- Quality of life questionnaire

Blood and urine for exploratory biomarkers

Imaging

- MRI/ MRS of leg and arm muscles to measure muscle volume, T2 value and fat fraction
- DEXA scan at screening and at 6 months

Outcome measures:

- Comparing MRI/MRS changes the leg and arm muscles at screening and 6 months
- Change in 6 min walk test and 10 meter timed run test for ambulatory patients
- Change in strength assessment
- Change in FVC measurements

Strength assessment:

- MRC scale: Shoulder abduction, elbow flexion, knee extension and knee flexion, hip flexion, foot dorsiflexion.
- Grip strength (Jamar dynamometer)

- Hand held dynamometry

Functional testing:

- Lift arm above head
- Lift arm above head using 50g/100g/200g/500g weight
- Bring arm to the mouth
- Bring weight to mouth using 50g/100g/200g/500g weight

STUDY INTERVENTION(S) / INVESTIGATIONAL AGENT(S):

Oral prednisone is a synthetic glucocorticoid that is FDA-approved medication for the treatment of various inflammatory and allergic conditions.

In this study, subjects will be asked to take weekly GC oral prednisone, dosed based on weight (1mg/kg for patients who weigh less than or equal to 70 kg and 0.75 mg/kg for patients who weigh more than 70 kg). Subjects will be instructed to take weekly prednisone on Mondays after their last meal between 7 and 9 PM. Study drug, oral prednisone, will be stored under the secure and controlled environment of the Investigational Drug Pharmacy at Northwestern Memorial Hospital. The Investigational Drug Pharmacy will follow its current SOP regarding the storage and handling of investigative drugs. The study drug will be dispensed from the Pharmacy and administered to subjects once they have signed informed consent, passed screening, on Day 0 of their treatment. Subjects will return home with 6 months of study drug treatment. They will be educated on dosing, storage, and return of unused study drug by the study staff. Subjects will be contacted on a monthly basis to assess medication and dosing adherence. They will be asked to confirm their medication and the dosing instructions and re-educated if not adhering.

PROCEDURES INVOLVED:

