This is an open label study that evaluates the safety and efficacy of oral weekly glucocorticoid steroids in patients with BMD and LGMD over 6 months. The study is comprised of three visits; screening to determine eligibility, initial dosing (Day 0), and final dosing (Month 6).

Screening

All subjects will be recruited to the study through the Muscular Dystrophy (MDA) Clinic at Northwestern Memorial Hospital. Prior to any study procedures, the study team will complete the full informed consent process with each patient. Upon obtaining informed consent, the study team will collect information from the patient including: demographics, vital signs, weight, height, medical history, concomitant medication, genetic mutation test results, EKG and Echocardiogram test results. If the subject does not have EKG or Echocardiogram results within the last 2 and 6 months, respectively, they will not be screened until they complete these two procedures as part of their standard of care. The principal investigator will review this information and determine whether the subject is eligible to participate in the study. If the subject is ineligible, he/she will be notified and continue to seek treatment through their treating physician.

Data will be retained in paper source materials by members of the study team at [name].

Day 0

Subjects will return to the MDA Clinic at Northwestern Memorial Hospital for the Day 0 procedures. If on a separate day from the screening visit, the study team will review concomitant medications, medical history, and collect vital signs with height and weight.

The following laboratory tests will be collected for safety purposes: A comprehensive chemistry panel, hemoglobin A1C, CK, and lipid panel. A blood and urine sample will be taken for exploratory biomarkers. Samples will be collected by members of the study team and processed by the Northwestern Memorial Hospital Main Laboratory. Records will be populated in the patient's medical charts and stored by members of the study team in the subject binders.

A member of the study team will also collect forced vital capacity in a sitting and supine position.

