7. A diagnosis of congestive heart failure
8. A diagnosis of chronic kidney disease
9. A diagnosis of untreated hypothyroidism
10. The patient is believed to be at high risk of osteoporosis by the primary investigator
11. Inability to provide consent
12. Prior oral glucocorticoid steroid use for > than one month during a subject's life.
13. Full time ventilator dependency
14. Heart failure symptoms or LVEF <25%
15. Orthopedic surgery within the prior year or upcoming elective orthopedic surgery within the 6-months from Day 0.
16. Inability to complete MRI (claustrophobia, metal implants)
17. Pregnant women at screening, women seeking to become pregnant, or men seeking to father a child within 6-months from Day 0 should not participate in this study.

PARTICIPANT POPULATION(S)

| Accrual Number: | Category/Group: (Adults) | Consented: Maximum Number to be Consented or Reviewed/Collected/Screened | Enrolled: Number to Complete the Study or Needed to Address the Research Question |
|-----------------|--------------------------|--|---|
| Total: | 50 adults | 40 adults | 30 adults |

RECRUITMENT METHODS

All subjects will be recruited through the Muscular Dystrophy (MDA) clinic at Northwestern Memorial Hospital. The MDA clinic is located in the [name] and is held on Wednesday mornings from 08:00-12:00.

Participants will be selected by the neurologists in the MDA clinic, primarily the Principal Investigator. They will be selected for screening based on their clinical exam, medical history, and willingness to participate in the study. The Principal Investigator will review the patient's medical chart to determine pre-eligibility. A member of the study team will conduct the informed consent process once pre-eligibility is confirmed by the Principal Investigator.

No external methods will be used for recruitment purposes.

COMPENSATION FOR PARTICIPATION IN RESEARCH ACTIVITIES

Subjects will not be compensated for participating in this study. Furthermore, subjects will not be reimbursed for expenses related to travel, lodging, or accommodation.

If patients become ill or are injured as a result of this study (medications, devices or procedures), they should seek medical treatment through their doctor or treatment center of choice. The subject should promptly tell his/her study doctor about any illness or injury.

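### Exclusion 17 bars pregnant women, but no pregnancy test is listed before the full six-month prednisone supply is dispensed on Day 0

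*Protocol*

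**What the plan says.** Under Inclusion and Exclusion Criteria, exclusion 17 keeps out "Pregnant women at screening, women seeking to become pregnant, or men seeking to father a child within 6-months from Day 0". The exclusion list is headed as collected at screening. Adults of either sex aged 18 to 65 may enrol.

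The protocol describes the baseline laboratory work in four places:
- **Study outline in Background:** a "blood sample for baseline screening including serum chemistries, HgbA1-C, creatine kinase, and lipid panel", plus exploratory biomarkers.
- **Study Endpoints, safety monitoring:** "Comprehensive chemistry panel, hemoglobin A1C, CK, lipid panel at screening and after 6 months of GC steroid dosing".
- **Procedures Involved, Day 0:** the same four items, with blood and urine for exploratory biomarkers.
- **Laboratory footnote to Table 1.0:** the same four items again.

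On the drug, Study Intervention(s) says that it is dispensed and "administered to subjects once they have signed informed consent, passed screening, on Day 0 of their treatment", and then: "Subjects will return home with 6 months of study drug treatment". Table 1.0 marks dispensing at Day 0 only. Until Month 6 the only further scheduled contact is a monthly telephone call about changes in health and how the drug is being taken.

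**The concern.** The protocol has a safety exclusion, but it schedules nothing that could detect the excluded condition when the woman does not know of it. Early pregnancy can be absent from both the history and the chart. If the plan is followed exactly, a woman with an unrecognised pregnancy passes screening, has the Day 0 procedures, receives the drug and goes home with all of it. Day 0 is the last scheduled point at which a test could prevent exposure, because no visit and no laboratory sample falls between Day 0 and Month 6.

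The stake is participant safety. No endpoint or estimate depends on it.

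**Working it through.** No figure in the protocol needs reproducing. The check is to follow a woman with an unrecognised pregnancy through each step before dispensing.

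| Step | What the protocol lists | Could it reveal an unrecognised pregnancy? |
|---|---|---|
| Screening visit | Demographics, vital signs, weight and height, history, medication, genetic result, EKG and echo review | No: no blood or urine is listed |
| Day 0, if on a separate day | "the study team will review concomitant medications, medical history, and collect vital signs with height and weight" | No: history reveals only what is known |
| Day 0 safety laboratory tests | Chemistry panel, HbA1c, CK, lipids | No pregnancy test is named |
| Day 0 urine | Exploratory biomarkers | Not stated to include a pregnancy test |
| MRI safety questionnaire | Medical and surgical history | Not stated to cover pregnancy; no test |
| Table 1.0 | No pregnancy-test row | No |

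Table 1.0 is not a complete list of procedures: the exploratory biomarkers have no row either. Its silence alone would prove little. The point rests on the procedures text and the laboratory lists being silent as well. Pregnancy tests listed: 0 across 3 visits. Dispensing occasions: 1, for the full supply.

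**DEXA.** Table 1.0 places the baseline scan at Day 0. Study Timelines has subjects return for one if they have had none in the previous 6 months, so it may also precede Day 0. Either way, no test comes before it. The protocol gives 4 mrem per scan and calls the exposure small.

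**Doses before the first call.**
- Day 0 takes place in the clinic ("Subjects will return to the MDA Clinic at Northwestern Memorial Hospital for the Day 0 procedures"), and Recruitment Methods says that the clinic is held on Wednesdays. Assume a Wednesday Day 0.
- Procedures Involved and Study Timelines both treat Day 0 as the first dosing: 1 dose.
- Thereafter: "Subjects will be instructed to take weekly prednisone on Mondays after their last meal between 7 and 9 PM". From a Wednesday, Mondays fall on Days 5, 12, 19, 26 and 33.
- Assume that the first monthly call is at Day 28 to 31. Four Monday doses (Days 5, 12, 19, 26) precede it.
- Total: 1 + 4 = 5 doses.

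The call is not an endpoint for this exposure. It asks about health changes and drug-taking, so a pregnancy still unrecognised then could go on being dosed.

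**The case against.** The strongest reply is that this is an omission and not a contradiction. Exclusion 17 does not say that pregnancy is to be excluded by test, and other exclusions, such as past tuberculosis, kidney disease and untreated hypothyroidism, also rest on history and chart review. A reader might infer that the protocol breaks a testing requirement of its own. It does not, because it states none. What remains is that those other exclusions are largely recorded diagnoses, whereas an early pregnancy may be unknown to everyone. The protocol also shows that it can insist on objective evidence: it will not screen a subject until a recent EKG and echocardiogram exist.

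A second reply is that safeguards exist. History is reviewed again when Day 0 is a separate day, the MRI questionnaire can make a subject ineligible, and the investigator may withdraw anyone thought to be at risk of harm. This stands for a known pregnancy. A reader might infer from the words about screening in exclusion 17, with a screening window that Table 1.0 appears to set at up to 2 months, that a woman who becomes pregnant before Day 0 must be dosed. The documents do not support that: a known pregnancy can be acted on. That wording is mostly a drafting gap.

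Third, a test might be described in consent material or site procedures that are not in view. That cannot be ruled out, so the point is limited to the criteria, the procedures text and the schedule.

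**Conclusion.** The point holds as a gap in enforcing the protocol's own safety exclusion. As written, the schedule cannot find an unrecognised pregnancy before the full supply is dispensed, nor before a baseline study DEXA.

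Its size can be stated only in part. About 5 doses would precede the first monthly call, given first dosing on Day 0, a Wednesday Day 0 and a call at Day 28 to 31; exposure could continue after that. A reader might go on to infer an expected number of exposed pregnancies or a rate of fetal harm. Neither can be derived: the protocol does not give the number of women of childbearing potential and names no fetal risk. Nor is there any consequence for the safety or efficacy comparisons between study entry and 6 months.

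This is a cheap improvement worth making, not a flaw that undermines the trial.

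**What to change.** - Add a row to Table 1.0 and a sentence to the Day 0 procedures: a urine or serum pregnancy test in women of childbearing potential, with a negative result required before drug is dispensed.
- Where the baseline study DEXA is done before Day 0, require a negative test before that scan too.
- Reword the opening of exclusion 17 to *pregnant at screening or Day 0*.

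Blood and urine are already taken on Day 0, but the urine is assigned to exploratory biomarkers. The protocol must therefore name the test and require a same-day result.

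The cost is one low-cost assay per woman of childbearing potential, a second if her DEXA comes first, a short wait before dispensing, and an occasional exclusion on Day 0, which the protocol already intends. The change does not address conception during the six months of treatment, which is a separate matter.
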